14.4 Ethical Conduct of the Trial

This trial will be conducted in accordance with the ethical principles that have their origins in the Declaration of Helsinki, in compliance with the approved protocol, ICH-GCP, and applicable regulatory requirements.

14.5 Subject Information and Consent

The investigator (or the person delegated by the investigator) will obtain a freely given written consent from each subject after an appropriate explanation of the aims, methods, anticipated benefits, potential hazards, and any other aspects of the trial which are relevant to the subject's decision to participate. The trial subject must be given ample time to consider participation in the trial, before the consent is obtained. The Informed Consent Documents must be signed and dated by the subject and the investigator who has provided information to the subject regarding the trial before the subject is exposed to any trial-related procedure, including screening tests for eligibility.

The investigator (or the person delegated by the investigator) will explain that the subject is completely free to refuse to enter the trial or to withdraw from it at any time, without any consequences for her further care and without the need to justify her decision. The subject will receive a copy of the Subject Information and her signed Informed Consent Form.

If new information becomes available that may be relevant to the trial subject's willingness to continue participation in the trial, a new Subject Information and Informed Consent Form will be forwarded to the IEC(s)/IRB(s) (and regulatory authorities, if required). The trial subjects will be informed about this new information and re-consent will be obtained.

Each subject will be informed that the monitor(s), quality assurance auditor(s) mandated by Ferring, IRB/IEC representatives or regulatory authority inspector(s), in accordance with applicable regulatory requirements, may review her source records and data. Data protection will be handled in compliance with national/local regulations.

For subjects not qualified to give their legal consent, the written informed consent must be obtained from the legal parent or guardian in accordance with national/local regulations. If such subjects can understand the risks and benefits of the trial, they should also be informed and provide their written assent.

14.6 Compliance Reference Documents

The Helsinki Declaration, the consolidated ICH-GCP, and other national laws in the countries where the trial takes place shall constitute the main reference guidelines for ethical and regulatory conduct.

15 LIABILITIES AND INSURANCE

15.1 ICH-GCP Responsibilities

The responsibilities of Ferring, the monitor and the investigator will be as defined in the ICH-GCP consolidated guideline, and applicable regulatory requirements in the country where the trial takes place. The investigator is responsible for adhering to the ICH-GCP responsibilities of investigators, for dispensing the IMP in accordance with the approved protocol or an approved amendment, and for its secure storage and safe handling throughout the trial.

15.2 Liabilities and Insurance

In case of any damage or injury occurring to a subject in association with the IMP or the participation in the trial, Ferring has contracted an insurance that covers the liability of Ferring, the investigator and other persons involved in the trial in compliance with the laws in the countries involved.

16 ARCHIVING

16.1 Investigator File

The investigator is responsible for maintaining all the records that enable the conduct of the trial at the site to be fully understood, in compliance with ICH-GCP. The trial documentation including all the relevant correspondence should be kept by the investigator for at least 15 years (or longer if so required by local law) after the completion or discontinuation of the trial, if no further instructions are given by Ferring.

The investigator is responsible for the completion and maintenance of the confidential subject identification code that provides the sole link between named subject source records and anonymous CRF data for Ferring. The investigator must arrange for the retention of this Subject Identification Log and signed Informed Consent Documents for at least 15 years (or longer if so required by local law) after the completion or discontinuation of the trial.

No trial site document may be destroyed without prior written agreement between the investigator and Ferring. Should the investigator elect to assign the trial documents to another party, or move them to another location, Ferring must be notified. Documents may be transferred to Ferring Global Quality Assurance, for example, if the investigator retires and the documents no longer can be archived by the site.

16.2 Trial Master File

Ferring will archive the trial master file in accordance with ICH-GCP and applicable regulatory requirements.

Day	____/____/____ mm dd yyyy	____:____ hr min  AM  PM	This is an unspecified day. It can be included if applicable.
Day	____/____/____ mm dd yyyy	____:____ hr min  AM  PM	This is an unspecified day. It can be included if applicable.
LH Surge Testing and Detection with Clearblue® Ovulation Kit	Date Clearblue testing began: ____/____/____ mm dd yyyy		
	Date Clearblue testing is positive: ____/____/____ mm dd yyyy		
Sexual Intercourse: You must engage in sexual intercourse on the day that your Clearblue test is positive, on the day following your positive test, and per your doctor's instruction after that. Enter the date(s) of sexual intercourse below for each day that applies.			
Day	Date	Did you have sexual intercourse on this day?	
Day of positive Clearblue test	____/____/____ mm dd yyyy	 Yes	 No
1 day after positive Clearblue test	____/____/____ mm dd yyyy	 Yes	 No
2 days after positive Clearblue test	____/____/____ mm dd yyyy	 Yes	 No
3 days after positive Clearblue test	____/____/____ mm dd yyyy	 Yes	 No
ADDITIONAL NOTES: _____ _____ _____ _____

Statistical Analysis Plan

Title of trial: A Multicenter, Double-Blind, Randomized, Placebo-Controlled Study Evaluating Three Doses of Subcutaneous Pulsatile GnRH Administered via OmniPod Pump for Ovulation Induction in Female Subjects with Primary Amenorrhea with Hypogonadotropic Hypogonadism NCT number: NCT01976728 Sponsor trial code: 000070 Date: 07 Dec 2017

Date: 07 Dec 2017 E-Statistical Analysis Plan-21977; Ver.1.0 Supersedes: None Page 1 of 59

STATISTICAL ANALYSIS PLAN

A Multicenter, Double-Blind, Randomized, Placebo-Controlled Study Evaluating Three Doses of Subcutaneous Pulsatile GnRH Administered via OmniPod Pump for Ovulation Induction in Female Subjects with Primary Amenorrhea with Hypogonadotropic Hypogonadism

Trial Code 000070

Investigational Product:	LutrePulse OmniPod
Indication:	Primary Hypothalamic Amenorrhea
Phase:	III
Author:	
Date of issue:	December 7, 2017
Version:	Amendment 1

The information in this document is confidential and is proprietary to Ferring Pharmaceuticals A/S or another company within the Ferring Group. It is understood that information in this document shall not be disclosed to any third party, in any form, without prior written consent of an authorised officer of Ferring Pharmaceuticals A/S or another company within the Ferring Group

Date: 07 Dec 2017 E-Statistical Analysis Plan-21977; Ver.1.0 Supersedes: None Page 2 of 59

Change log

Version No.	Effective Date	Reason for the Change / Revision	Supersedes
V1.0	Jul 11, 2017	SAP based on Protocol Amendment 6 dated June 30, 2017.	
Amend ment 1	Dec 7, 2017	 Per protocol amendment 7, the definition for the primary efficacy endpoint of ovulation is changed. Subjects who had a confirmed positive serum β-hCG (i.e., 2 positive results) or presence of a gestational sac documented by transvaginal ultrasound (TVUS) is considered as ovulatory, even if the subject did not have any post-baseline P4 ≥6 ng/mL. The positive LH surge rate is added as a secondary efficacy endpoint. 	V1.0

TABLE OF CONTENTS

TAB	LE OF	CONTENTS	3
1	Introd	duction	6
	1.1	Definitions/ Abbreviations	
		1.1.1 Definition of Terms	6
		1.1.2 Abbreviations	6
2	Trial (Objectives and Endpoints	8
_	2.1	Primary Objective	
	2.2	Secondary Objectives	
	2.3	Primary Endpoint.	
	2.4	Secondary Endpoints	
		2.4.1 Progesterone Level	8
		2.4.2 Pregnancy	8
		2.4.3 Ovarian Follicular Development	8
		2.4.4 Luteal Phase Support	9
		2.4.5 Pharmacodynamic (PD) Endpoints	9
		2.4.6 Safety Endpoints	9
3	Trial o	design	.10

This document describes the data analysis specifications for Ferring Pharmaceuticals protocol LutrePulse OmniPod titled: "A Multicenter, Double-Blind, Randomized, Placebo-Controlled Study Evaluating Three Doses of Subcutaneous Pulsatile GnRH Administered via OmniPod Pump for Ovulation Induction in Female Subjects with Primary Amenorrhea with Hypogonadotropic Hypogonadism". This version of the statistical analysis plan dated December 7, 2017 was prepared in accordance with the protocol LutrePulse OmniPod, Trial ID 000070, Amendment 7, dated December 6, 2017. Other related documents are the electronic case report form (eCRF), data definition fields and data set definitions.

The purpose of this Statistical Analysis Plan (SAP) is to provide greater and more technical details of the pre-planned statistical analyses described in the statistical section of the Clinical Trial Protocol. It aims to answer the protocol objectives in a statistically rigorous fashion using methods identified prior to database lock. Any deviations from these methods must be documented in the final clinical study report. Specifications of tables, figures, and data listings are contained in a separate document (Table shells).

1.1 Definitions/Abbreviations

1.1.1 Definition of Terms

Terms	Definitions
Randomised	Subject randomised to trial treatme

Screened Subject randomised to trial treatment Subject who enters the screening phase

OmniPod A disposable delivery pump for drug delivery with a handheld

wireless controller (the Manager) for SC drug delivery

OmniPod Manager A wireless, handheld device that programs the OmniPod with the

subject's LutrePulse delivery instructions and wirelessly monitors

the OmniPod's operation

Unblinded Coordinator Assigned by the investigator prior to the start of the study and

will be unblinded to the subject's study drug assignment (dose only) and will be responsible for the set-up of the OmniPod

Manager, distribution and accountability of the drug.

1.1.2 Abbreviations

Abbreviations	Meaning of abbreviations in document
Addreviations	vieaning of addreviations in document

AE Adverse Event

ANCOVA Analysis of Covariance

ATC Anatomical-Therapeutic-Chemical

GLM General Linear Model

ITTIntent-to-TreatFASFull Analysis SetPPSPer-Protocol Set

SAS Statistical Analysis System

NPAR1WAY Non-Parametric One-Way Analysis of Variance

IMP Investigational Medicinal Product

Ferring Pharmaceuticals

CONFIDENTIAL

Gonadorelin Acetate, FE 999037, FE 999903

Trial Code: 000070 Statistical Analysis Plan Date: 07 Dec 2017 E-Statistical Analysis Plan-21977; Ver. 1.0 Supersedes: None Page 7 of 59

Abbreviations Meaning of abbreviations in document

HH Hypogonadotropic Hypogonadism

LH Luteinizing Hormone

eCRF Electronic Case Report Form FSH Follicle-Stimulating Hormone

ECG Electrocardiography

E2 Estradiol
P4 Progesterone
PRL Prolactin

TSH Thyroid-Stimulating Hormone
TVUS Transvaginal Ultrasound
FHM Fetal Heart Movement

GnRH Gonadotropin-Releasing Hormone

CT Computed Tomography

MedDRA Medical Dictionary for Regulatory Activities

MRI Magnetic Resonance Imaging mITT Modified Intent-to-Treat

β-hCG Beta human Chorionic Gonadotropin

Date: 07 Dec 2017 E-Statistical Analysis Plan-21977; Ver.1.0 Supersedes: None Page 8 of 59

2 Trial Objectives and Endpoints

2.1 Primary Objective

• To compare the ovulation rate in women with primary amenorrhea with hypogonadotropic hypogonadism (HH) following each of 3 doses (10 μg, 15 μg, and 20 μg per pulse) of subcutaneous pulsatile gonadotropin-releasing hormone (GnRH) administered with the LutrePulse OmniPod Pump versus placebo

2.2 Secondary Objectives

- To evaluate clinical pregnancy rate
- To evaluate biochemical pregnancy rate
- To evaluate positive LH surge rate
- To evaluate ovarian follicular development
- To evaluate luteal phase support with GnRH
- To evaluate pharmacodynamic parameters
- To evaluate the safety of LutrePulse OmniPod SC

2.3 Primary Endpoint

• Ovulation rate, calculated as a proportion of subjects with at least 1 post-baseline progesterone (P4) level ≥ 6 ng/mL as measured by a central laboratory a confirmed positive serum β -hCG (i.e., 2 positive results) or presence of a gestational sac documented by transvaginal ultrasound (TVUS).

2.4 Secondary Endpoints

2.4.1 Progesterone Level

• Proportion of subjects with at least 1 post-baseline progesterone (P4) level ≥ 10 ng/mL

2.4.2 Pregnancy

Clinical pregnancy rate

• Proportion of subjects with presence of gestational sac and fetal heart movement (FHM) on transvaginal ultrasound (TVUS) at approximately 2 to 4 weeks after second positive serum beta human chorionic gonadotropin (β-hCG) test

Biochemical pregnancy rate

• Proportion of subjects with a confirmed positive (i.e., 2 positive results) serum beta human chorionic gonadotropin (β-hCG) test 14 + 4 days post LH surge

2.4.3 LH surge detection

• Proportion of subjects with a positive detection of LH surge on their Clearblue tests

2.4.4 Ovarian Follicular Development

- Number of follicles with a mean diameter ≥ 14 mm
- Number of dominant follicles with a mean diameter ≥ 18 mm

2.4.5 Luteal Phase Support

- Maximum P4 levels from Days 19, 21, 23, 25, and 27
- Mean P4 levels from Days 19, 21, 23, 25, and 27

2.4.6 Pharmacodynamic (PD) Endpoints

- FSH and LH change from baseline in relation to the first GnRH pulse on Day 1 and Day 10
- Mean serum FSH and LH levels on Day 1 and Day 10
- Estradiol (E2) serum levels on Day 1 and Day 10

2.4.7 Safety Endpoints

- Adverse events (type, frequency, causality, intensity and seriousness)
- Clinical chemistry, haematology, urinalysis
- Frequency and severity of ovarian hyperstimulation syndrome (OHSS)

Date: 07 Dec 2017 E-Statistical Analysis Plan-21977; Ver.1.0 Supersedes: None Page 10 of 59

3 Trial design

This multicenter, randomized, double-blind, placebo-controlled study will be performed in women with primary amenorrhea with HH who desire pregnancy. Subjects with primary amenorrhea with HH will be treated with 1 of 3 doses of pulsatile GnRH or placebo, administered SC via the OmniPod pump manufactured by Insulet. The treatment duration with LutrePulse OmniPod SC or placebo can be approximately 5 weeks. It is expected that the response to treatment will occur within 2 to 3 weeks after therapy initiation. When LH surge is detected by urine kit, therapy should be continued for approximately another 2 weeks to maintain corpus luteum (continue until confirmatory serum pregnancy test). Subjects will discontinue treatment either at the onset of menses or negative or positive confirmatory serum pregnancy test. Subjects will be required to return to the study site for pharmacodynamic blood draws, TVUS, serum pregnancy tests, and safety follow-up assessments.

The study will consist of 3 periods: Screening (includes progestin challenge test), Treatment (includes pituitary priming and treatment phase), and Follow-up.

3.1 General Design Considerations

Approximately 60 subjects will be randomly assigned to 1 of 4 treatment arms:

- LutrePulse OmniPod SC 10 µg (Test Product)
- LutrePulse OmniPod SC 15 μg (Test Product)
- LutrePulse OmniPod SC 20 µg (Test Product)
- Placebo (10, 15, or 20 µg /pulse as a fixed "dose")

Subjects will receive consecutive pulses of GnRH or placebo, each delivered at 90-minute intervals, for up to 37 days of treatment. Each OmniPod will be worn for 3 full days (Days 1-3, 4-6, 7-9, etc. up to Day 37) and will be replaced every 4th day (i.e., Day 4, Day 7, Day 10, etc.). New OmniPod pumps should be applied at approximately the same time as the first pump. Randomized fixed doses of either 10 μ g, 15 μ g, or 20 μ g will be programed into the OmniPod Manager and subcutaneously delivered to the subject. For every 10 μ g, 15 μ g, or 20 μ g dose the subject will receive 10 μ L, 15 μ L, or 20 μ L amount of volume with the same concentration of drug per pulsatile injection. Placebo doses will receive the same amount of volume respectively as the Lutrepulse OmniPod dose without active drug substance.

3.2 Determination of Sample Size

The sample size was determined based on the original fixed parallel group study design. The true ovulation rate for LutrePulse OmniPod SC 20µg, 15µg, 10µg, and placebo was assumed to be 70%, 65%, 60%, and 1%, respectively. Under these assumptions, a sample size of 14 subjects per group (total 56 subjects) will provide at least 80% power to detect differences between LutrePulse OmniPod SC 20µg and placebo, 15µg and placebo, and 10µg and placebo in ovulation rate separately with the stratified one-sided Fisher's exact tests at an overall significance level of 0.025 with the closed testing procedure (Kong et al., 2005). Approximately 60 subjects will be randomized by assuming up to 4 subjects may be ineligible to the Full Analysis Set.

Date: 07 Dec 2017 E-Statistical Analysis Plan-21977; Ver. 1.0 Supersedes: None Page 11 of 59

3.3 Randomization, Blinding, and Replacement of Subjects

All eligible subjects will be randomly assigned at least 3 days before Treatment Day 1, based on the computer-generated randomization list provided by the designated unblinded statistician. Any relevant information pertaining to the generation of the randomization list including the block size will only be communicated from the sponsor to the unblinded statistician.

The first 15 eligible subjects will be randomly assigned to 1 of 3 treatment arms: LutrePulse OmniPod SC 10 µg, LutrePulse OmniPod SC 20 µg, or OmniPod SC placebo in a 1:1:1 ratio. The subsequent 25 eligible subjects will be randomly assigned to LutrePulse OmniPod SC 10 µg, LutrePulse OmniPod SC 15 µg, LutrePulse OmniPod SC 20 µg, or OmniPod SC placebo in a 1:2:1:1 ratio. The rest of the eligible subjects will be randomly assigned to LutrePulse OmniPod SC 10 µg, LutrePulse OmniPod SC 15 µg, LutrePulse OmniPod SC 20 µg, or OmniPod SC placebo in a 1:1:1:1 ratio.

To maintain the blind, the placebo subjects will be randomized to the equivalent dosing setting in the Manager for 10 μ g /pulse or 20 μ g /pulse for the first 15 eligible subjects and 10 μ g /pulse, 15 μ g /pulse, or 20 μ g /pulse for the subsequent randomization schemes.

Table 1 displays the estimated number of subjects randomized to each treatment arm. The three placebo groups with different dose settings will be pooled as a single placebo group for all data summaries and analyses. The LutrePulse 20 μg will be compared to (Placebo I + Placebo II + Placebo III), LutrePulse 15 μg will be compared to (Placebo II + Placebo III), and LutrePulse 10 μg will be compared to (Placebo II + Placebo III).

The randomization assignment will be available to the OmniPod Manager programmer (Unblinded Coordinator) with respect to dose only (but will remain blinded to assigned study drug, whether active or placebo). The randomization assignment will not be available to any other site personnel involved in the conduct and evaluation of the study until the study database is declared clean and is released to the statistician.

Subjects who discontinue early from the study for any reason will not be replaced.

 Table 1
 Treatment arms

Treatment Arm	Treatment	Estimated # of Patients Entering Treatment	Formulation and Dose of Study Drug	Frequency	Admin. Route
LutrePulse OmniPod SC 20 µg	LutrePulse 20 μg/pulse	15	20 μg dose in white powder reconstituted in 20 μL saline with 0.9% sodium chloride	90-minute intervals daily	SC pulsatile injection Via OmniPod pump
LutrePulse OmniPod SC 15 µg	LutrePulse 15 μg/ pulse	15	15 μg dose in white powder reconstituted in 15 μL saline with 0.9% sodium chloride	90-minute intervals daily	SC pulsatile injection Via OmniPod pump

Ferring Pharmaceuticals

CONFIDENTIAL

Gonadorelin Acetate, FE 999037, FE 999903 Trial Code: 000070

Statistical Analysis Plan

Date: 07 Dec 2017 E-Statistical Analysis Plan-21977; Ver. 1.0 Supersedes: None Page 12 of 59

LutrePulse OmniPod SC 10 µg	LutrePulse 10 μg/pulse	15	10 μg dose in white powder reconstituted in 10 μL saline with 0.9% sodium chloride	90-minute intervals daily	SC pulsatile injection Via OmniPod pump
OmniPod SC Placebo I	Placebo 20 μg / pulse	5	20 μL saline with 0.9% sodium chloride	90-minute intervals daily	SC pulsatile injection Via OmniPod pump
OmniPod SC Placebo II	Placebo 15 μg / pulse	5	15 μL saline with 0.9% sodium chloride	90-minute intervals daily	SC pulsatile injection Via OmniPod pump
OmniPod SC Placebo III	Placebo 10 μg / pulse	5	10 μL saline with 0.9% sodium chloride	90-minute intervals daily	SC pulsatile injection Via OmniPod pump

Date: 07 Dec 2017 E-Statistical Analysis Plan-21977; Ver.1.0 Supersedes: None Page 13 of 59

4 Subject Disposition

The number and percentage of randomized subjects treated with Investigational Medicinal Product (IMP), prematurely discontinued, and completing the study will be summarized.

A subject who has an increased risk of developing multiple gestation/OHSS (4 or more follicles with a mean diameter ≥ 15 mm by TVUS and E2 levels ≥ 1200 pg/mL) will be immediately discontinued from treatment. In addition, any clinically important adverse physical or symptomatic findings/events and/or abnormal laboratory findings that are above the pre-specified critical values defined in the laboratory manual will be grounds for discontinuation from the study. Subjects who fail to respond to study treatments (no LH surge) and withdraw from study treatments with less than 14 days of study treatment exposure will be considered as an early discontinuation. For subjects with at least 14 days of study treatment exposure, the end of study visit is required for the subject to be considered as a completer.

All post-baseline discontinuations will be summarized by reason for early termination. Subjects screened but not randomized/allocated to treatment will be presented with the reason(s) for screen failure in a data listing. All withdrawals from trial will be summarised with frequency and percentage for each category of withdrawal reason.

Gonadorelin Acetate, FE 999037, FE 999903 Trial Code: 000070

Statistical Analysis Plan

Date: 07 Dec 2017 E-Statistical Analysis Plan-21977; Ver.1.0 Supersedes: None Page 14 of 59

5 Protocol Deviations

The criteria for protocol deviations considered major with the implication of data exclusions from the per-protocol analysis set will be identified and documented by Ferring clinical team/project management based on a review of data listings prior to database lock.

Major protocol deviations may include major violations of the inclusion/exclusion criteria, missing randomization, errors in treatment assignment, significant noncompliance to the dosing administration, or other serious violations.

Number and percentage of subjects with any major and minor deviations will be tabulated for each category of protocol deviation for descriptive purposes by treatment group.

6 Analysis sets

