9.1 General Considerations

Sites from all countries/regions (US, Canada) will be pooled for all analyses. No stratification by site will be made in the analysis.

Unless otherwise noted, data will be summarized in tabular format by treatment group using summary tables and data listings. All study data documented on the eCRFs will be included in the study data listings.

All efficacy analyses will be conducted for the FAS. The three placebo groups with different dose settings will be pooled as a single placebo group for all efficacy summaries and analyses.

Continuous variables will be described with the number of non-missing values, mean, standard deviation (SD), median, and minimum/maximum values. Categorical variables will be described with the number and percentage of subjects with each level. Missing values will not be included in the calculation of percentages. All individual subject data will be listed.

The software used for all summary statistics and statistical analyses will be SAS Version 9.2 or later.

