10.1 General Considerations

Safety parameters will be evaluated for the Safety Analysis data set.

The three placebo groups with different dose settings will be pooled as a single placebo group for all safety summaries and analyses.

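### SAP 3.3 pools all three placebo settings, then compares 15 µg and 10 µg with only two of them; this exposes secondary and pharmacodynamic dose contrasts, not the primary test

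*SAP*

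**What the plan says.** SAP 3.3 states the general rule first: "The three placebo groups with different dose settings will be pooled as a single placebo group for all data summaries and analyses". The sentence after it assigns controls dose by dose. For 20 µg it reads "will be compared to (Placebo I + Placebo II + Placebo III), LutrePulse 15"; for 15 µg it continues "will be compared to (Placebo II + Placebo III), and LutrePulse 10"; and 10 µg also "will be compared to (Placebo II + Placebo III"). In SAP Table 1, Placebo I, II and III are the 20, 15 and 10 µg pump settings, with an estimated 5 subjects each.

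Two later sections repeat the general rule. SAP 9.1 says that the placebo groups "will be pooled as a single placebo group for all efficacy summaries and analyses", and SAP 10.1 that they "will be pooled as a single placebo group for all safety summaries and analyses". The sections that specify individual analyses (SAP 9.2 to 9.4) refer only to placebo, the placebo group or the placebo arm, without naming settings.

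**The concern.** The two sentences in SAP 3.3 cannot both be programmed for 15 µg or 10 µg. One keeps the Placebo I subjects as controls and the other drops them.

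The documents give no ground for dropping them. By Table 1 the settings differ only in the volume of saline delivered (20, 15 or 10 µL), and SAP 3.3 and Protocol 5.4.1 say they exist to protect the blind. No obvious rule produces the subset as written:

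- Matching on volume would pair 15 µg with Placebo II alone and 10 µg with Placebo III alone.
- Using settings no larger than the dose would leave 10 µg with Placebo III alone.
- Using only concurrent controls for 15 µg would drop the placebo subjects of the first scheme, whatever their setting, and would drop none for 10 µg.

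At stake are precision and comparability in the dose-by-dose analyses. If 20 µg is judged against one control group and the other doses against a smaller one, a chance peculiarity of about five Placebo I women could look like a difference between doses. Evaluating dose-response is the second stated objective of the adaptive design (SAP 9).

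**Working it through.** **1. The plan's own figure.** SAP 3.2 claims at least 80% power for each dose against placebo with 14 per group. The ovulation rates for 20, 15 and 10 µg and placebo "was assumed to be 70%, 65%, 60%, and 1%, respectively", and the test is a one-sided Fisher test at 0.025. Summing the exact binomial probabilities of all significant outcomes, without stratification, gives 99.4%, 98.4% and 96.4% for the three doses. At 0.025/3, a conservative stand-in for the closed procedure, it gives 97.8%, 95.1% and 90.5%. The claim is met. It assumes equal groups, that is, the full placebo arm for every dose. The current plan no longer tests ovulation dose by dose, so these powers do not measure the size of this problem.

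**2. Control group under each sentence, with the Table 1 counts.**

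| Dose | Pooling rule (SAP 3.3, 9.1, 10.1) | Subset sentence (SAP 3.3) |
|---|---|---|
| 20 µg | I + II + III = 5 + 5 + 5 = 15 | I + II + III = 15 |
| 15 µg | I + II + III = 15 | II + III = 5 + 5 = 10 |
| 10 µg | I + II + III = 15 | II + III = 10 |

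The share lost for 15 µg and 10 µg is 5/15 = 33%. These two doses share the same reduced control group; 20 µg differs from both.

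**3. Precision, unadjusted.** With equal variances and no covariates, the standard error of a dose-placebo mean difference is proportional to sqrt(1/n_dose + 1/n_placebo). With 15 per dose, the ratio is sqrt[(1/15 + 1/10) / (1/15 + 1/15)] = sqrt(0.1667/0.1333) = sqrt(1.25) = 1.118. Intervals would be about 12% wider, and 1 − 1/1.25 = 20% of the information would be lost.

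**4. Allowance for randomization scheme.** The planned analyses stratify by scheme (van Elteren test, SAP 9.3.4) or include it as a factor (ANCOVA, SAP 9.3.5 and 9.4). With 60 randomized, the SAP 3.3 ratios give 5 placebo subjects in each scheme (15/3, 25/5 and 20/4) and 0, 10 and 5 subjects on 15 µg. The first scheme has no 15 µg arm, so in the van Elteren test its placebo subjects add nothing to the 15 µg contrast. Only 10 controls are usable there even with full pooling.

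Assume that settings are split equally within scheme: two settings in the first, three later. Placebo I then takes 10/3 = 3.3 of those 10 controls and 6.7 remain. Weighting the two later schemes by n_dose × n_placebo / (n_dose + n_placebo):

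- Full pooling: (10 × 5)/15 + (5 × 5)/10 = 3.33 + 2.50 = 5.83.
- II + III only: (10 × 3.33)/13.33 + (5 × 3.33)/8.33 = 2.50 + 2.00 = 4.50.
- Standard error ratio: sqrt(5.83/4.50) = 1.14.

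Under the same assumption Placebo I would total 5/2 + 10/3 = 5.8 of 15, or 39%, rather than the 5 in Table 1. The unadjusted ratio with 15 − 5.83 = 9.17 controls would be sqrt[(1/15 + 1/9.17)/(2/15)] = 1.15. These are illustrations; the ANCOVA, with its other arms and baseline covariate, will not match them exactly.

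**5. Which analyses the sentence can reach.** It assigns controls to single doses, so it bears only on single-dose contrasts with placebo:

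- Exposed, for 15 µg and 10 µg: follicle counts (SAP 9.3.4), maximum and mean luteal progesterone (9.3.5), and FSH, LH and estradiol (9.4).
- Not exposed: the primary ovulation test (9.2.1), and progesterone ≥ 10 ng/mL, pregnancy and LH surge (9.3.1 to 9.3.3). All of these compare pooled 15 + 20 µg with placebo.
- Not exposed: the ED80 rule (SAP 9, inequality 2), which uses one observed placebo rate for every dose.

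**The case against.** The strongest reply is that this is a drafting slip in a randomization section and that the operative text already settles it. SAP 9.1 covers all efficacy analyses and 10.1 all safety analyses, and every analysis section refers to a single placebo group or arm. No section plans an analysis on Placebo II + III. The exposed contrasts are secondary or pharmacodynamic, and the 20 µg control is the same under either sentence. All of this stands, and it limits the weight of the point. It does not remove it: SAP 3.3 is the only place that spells out the control group for each dose, so a programmer could reasonably take it as the specific rule that overrides the general one.

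A second reply is that the 12% figure ignores stratification and uses counts that Table 1 labels as estimates. That also stands, and the figure is offered only as an unadjusted illustration.

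A reader might go further and infer that the primary test has two possible control groups. The documents do not support this. The subset sentence never mentions the pooled 15 + 20 µg group. SAP 9.2.1.2 describes the primary comparison as against the placebo arm, and SAP 15.2.4 works with 15 placebo and 30 pooled subjects. Example Trial 1 in SAP 15.2.2 reports p = 0.0052 for 10 responders against 0. That value comes from 18 pooled subjects against the whole placebo arm of 9: C(18,10)/C(27,10) = 43,758/8,436,285 = 0.0052. Even if 30 were compared with 10 at the 0.0131 threshold, power at 67.5% (the mean of 65% and 70%) against 1% would be 98.9%, compared with 99.9% for 30 against 15.

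**Conclusion.** The contradiction is real and lies in current SAP text. As written, the subset sentence conflicts with the sentence before it and with SAP 9.1 and 10.1, and nothing in either document justifies omitting Placebo I.

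If it were followed, the 15 µg and 10 µg contrasts in SAP 9.3.4, 9.3.5 and 9.4 would lose about a third of their planned controls, and 20 µg would be measured against a different control group. The standard error would rise by about 12% with the Table 1 counts, equal variances and no adjustment. The loss under the planned analyses may differ, especially for 15 µg; the illustrations with an equal split of settings give 14% to 15%.

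Nothing here threatens the primary conclusion, the pooled-dose secondary tests or dose selection by ED80. It should be corrected because it leaves the control group for several dose contrasts open to interpretation in a plan meant to fix methods before database lock. The point assumes that the approved SAP carries the sentence as it reads in the supplied text. A term lost in reproducing the document is possible but unlikely, since it would have to be missing from two clauses and intact in the third.

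**What to change.** Delete the sentence in SAP 3.3 that assigns placebo settings to each dose, or restate it so that 20, 15 and 10 µg are each compared with Placebo I + II + III, consistent with SAP 9.1. Check that the separate table shells and any analysis programs already written do not carry the subset rule.

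The cost is one SAP sentence. Sample size, data collection and the type I error argument do not change. Make the correction before anyone who chooses or programs the analyses sees unblinded data, so that the choice of control group cannot depend on the results.
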